This project will use an efficient 2x2x2x2 factorial design (Table 1) to identify reach-focused intervention components that either singly, or in combination, increase patient use of evidence-based smoking cessation treatment over 2 years of availability and, by extending treatment reach, reduce smoking prevalence 2 years after enrollment. All adult patients who smoke daily, but who are **not willing to enter smoking cessation treatment** at the time of enrollment (the vast majority of smokers⁴⁰) will be eligible to participate, with no obligation to quit smoking or use treatment. Participants (N=240-300) will be recruited in 4-12 primary care clinics in 2 healthcare systems by system staff using an opt-out strategy⁴¹ to maximize inclusion and enhance dissemination and the generalizability of results. (Roughly 60 additional patients who do not meet eligibility criteria for intensive counseling and medication with either combination NRT or varenicline will be included in the study but will not be part of the experimental sample.)

This will be the first factorial experiment in healthcare settings to test interventions designed to extend the reach of varied smoking cessation treatments in primary care patients who are not initially willing to make an aided quit attempt (see Table 1). This rigorous and efficient factorial design will address the following aims:

Primary Aims

1. To **create an optimized reach intervention package** by identifying intervention components that increase cessation treatment reach especially well, at low cost, at 1-year follow-up.
2. To estimate the **main and interactive effects** of the intervention components on cumulative treatment **reach over 2 years** of treatment access.

Secondary Aims

1. To estimate the main and interactive effects of intervention components on **abstinence** at 2-year follow-up.
2. To identify the degree to which intervention component effects on 2-year abstinence are **mediated by increases in cessation treatment reach**.
3. To assess the **cost-effectiveness** of intervention components in promoting reach and abstinence.
4. To identify patient and clinic **moderators** of intervention component effects on reach and abstinence.

III. METHODS

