The Care Manager will also ask if the participant gives the study permission to stay in touch with them and send them reminders about upcoming study contacts during the study via email and/or text message. The Care Manager will remind them that email and text messaging are generally not a secure way to communicate about their health as there are many ways for unauthorized users to access email and text messages. The Care Manager will also inform them that they do not have to provide their email address or text message number to participate in this study.

D. Randomization

Randomization will occur immediately after oral consent and baseline data are collected and will be conducted by healthcare system Tobacco Care Managers using randomization tables developed at UW-CTRI. Randomization will be blocked by clinic, patient-identified gender, and eligibility for randomization to intensive treatment access to ensure equitable distributions across conditions. Enrollees who meet initial eligibility for intensive treatment will be randomized to 1 of 16 conditions (see Table 3), while those who do not meet these criteria (e.g., those with a history of severe renal disease and allergic reaction to NRT) will be randomized to 1 of the first 8 conditions shown below (because the 4th factor, access to intensive treatment, will not apply to them; they will have access to counseling and medication, if appropriate, from the quitline and/or their primary care provider). No placebo will be used in this pragmatic trial. Every enrollee will receive advice to quit smoking and information about resources available to help

them quit smoking no less than 2 times per year for 2 years. All enrollees who want stop-smoking treatment at some point in the 2-year study will have access to no less than a single smoking cessation counseling session and a 2-week supply of a single nicotine replacement therapy (if medically eligible for nicotine medication).

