Aim 1. To develop an optimized package of health system interventions to promote smoking cessation treatment reach among patients not initially willing to quit, logistic regression analyses will be conducted with binary treatment initiation over 1 year of study enrollment as the primary outcome, in the primary sample randomized on all 4 experimental factors. Effect size estimates will be generated and all main and all 2-way, 3-way, and 4-way interactive effects will be tested as predictors in the logistic regression model. In addition, the magnitude of the difference in treatment initiation rates between the most promising intervention conditions and the cell in which all the intervention components are off will be used to generate an upper limit estimate of optimized reach intervention package effects. Exploratory analyses will be conducted adjusted for covariates known to be predictive of treatment use. Exploratory sensitivity analyses will be conducted to estimate intervention component effects across a range of assumptions regarding missing outcome data. We anticipate that 25% of follow-up data will be missing and will examine the robustness of results across intent-to-treat and less stringent assumptions regarding missingness (i.e., that 90%, 80%, or 70% of missing cases are smoking) in sensitivity analyses. We may also use multiple imputation and examine the consistency of results across multiply imputed datasets and those imputed using the simple methods already described. This analysis will use data collected via UW-CTRI staff during follow-up telephone interviews supplemented by data regarding smoking cessation attempts and treatment utilization extracted from the EHR and the WTQL.

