Aim 2. To assess the cumulative main and interactive effects of each intervention component on binary treatment initiation over 2 years of study enrollment, logistic regressions predicting any treatment initiation (defined as completing a first counseling session, the primary outcome at a more distal endpoint) will address this aim, first in the ~240-300 patients (max 300) eligible for intensive treatment to examine all 4 intervention components, and then, separately, in the ~30-60 (max 60) participants who do not meet criteria for access to intensive treatment. As in the analyses for Aim 1, effect coding will be used to ensure the independence of the main and interactive effects in this balanced design, exploratory analyses will be conducted with adjustment for covariates, and exploratory sensitivity analyses will examine the robustness of results across a range of missing data assumptions.

In addition to the binary logistic regression described above, exploratory logistic regression models will estimate intervention component main and interactive effects on treatment completion (all 3 counseling sessions and medication initiation) among those randomly assigned to have access to intensive treatment with C-NRT or varenicline and counseling. This exploratory analysis will quantify the effects of the informational/motivational intervention components on the dose of evidence-based treatment received by participants over 2 years. Effect coding, covariate adjustment, and sensitivity analyses will be used, as described above. Exploratory descriptive analyses of the frequency and temporal patterns of treatment use will also be conducted (e.g., to explore whether C-NRT use tends to follow varenicline more often than the reverse, to see whether C-NRT is more likely to be repeated than varenicline use). As for Aim 1, this analysis will use data collected via UW-CTRI staff during follow-up telephone interviews supplemented by data regarding smoking cessation attempts and treatment utilization extracted from the EHR.

Secondary Aim 1. Although the primary outcome in this study is treatment reach, the ultimate objective of this project is to help more smokers stop smoking. A key secondary binary logistic regression analysis in this project will estimate reach-focused intervention component effects on end-of-study 7-day point-prevalence abstinence confirmed by CO testing, and, if CO is elevated,

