salivary cotinine/anabasine testing, among those claiming abstinence. This analysis will estimate the main and interactive effects of the intervention components on end-of-study (2-year) 7-day point-prevalence abstinence rates (as ascertained by self-report and biochemically confirmed). The primary analysis will be an unadjusted, intent-to-treat analysis, but this will be followed by exploratory adjusted models and sensitivity analyses. This analysis will use data collected by personnel during the final semi-annual follow-up telephone interview plus the biochemical confirmation visit (for those claiming abstinence), supplemented by data on smoking status extracted from the EHR.

Additional, exploratory analyses will examine the 7-day point-prevalence abstinence rates at 3 time points following each round of treatment initiated with the Tobacco Care Managers (3, 12, and 26 weeks post-target-quit-day), for up to 4 rounds of treatment. Exploratory descriptive analyses will summarize abstinence rates at each time point, and the effects of intervention components on these abstinence rates will be explored, both within and across rounds of treatment. This analysis will use data collected by UW-CTRI personnel during the post-quit follow-up telephone interviews.

Secondary Aim 2. The degree to which intervention component effects on abstinence are mediated by treatment use will be examined via formal mediation analysis. These tertiary outcome models will examine the extent to which intervention component effects on 7-day point-prevalence abstinence after 2 years of enrollment are mediated by initiation of treatment in the preceding 2 years. Enrollees eligible for intensive treatment will be the primary sample for these analyses, with exploratory replication in those not eligible for intensive treatment. To examine mechanisms of specific intervention effects on the primary outcomes of interest, additional, exploratory models will examine the extent to which intervention components affect quitting motivation, self-efficacy, and perceived intra-treatment social support, and the degree to which these candidate mediators are associated with treatment initiation and point-prevalence abstinence at the end of the study. Within each treatment episode, the degree to which short-term abstinence (3-, 12-, or 26-weeks postquit) is mediated by reductions in withdrawal will also be explored.

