Supplemental Models. Exploratory GEE models may examine intervention component effects on the pattern of treatment initiation and abstinence across the 4 semi-annual follow-up waves. Additional, exploratory latent class analyses may examine patterns of engagement and abstinence in 6-month epochs over 2 years, conditional on intervention components and combinations. These supplemental analyses will be exploratory and hypothesis generating. Their results may facilitate interpretation of interaction effects in the primary analyses and inform refinement of optimized combinations of reach-focused system interventions.

Covariates. All models described above will be conducted and reported with and without adjustment for healthcare system or clinic and factors known to be associated with treatment engagement (e.g., sex, age, medical comorbidities related to smoking, healthcare utilization⁷³⁻⁷⁷). Covariates will be removed from final adjusted models if not significantly related to the dependent variable to enhance model parsimony.

Power and Sample Size

The target sample size for participants eligible for randomization to intensive treatment access ($N=1664$) was selected based on estimates of the flow of patients through clinics in a 9-month period and the number needed to detect at least an 8% increment in both treatment reach (defined here as initiation or completion of treatment) and 2-year abstinence rates, as we consider 8% to be a clinically meaningful increment in both reach and abstinence. Power estimates for main effects of each intervention component across a range of possible base rates in treatment use (from 5 to 65%) and abstinence (from 5 to 30%) exceed .9 (at alpha .05) with a sample of 1664 participants. Power to detect simple main effects (i.e., to interpret interactions) exceeds .7 for all but one combination of base rates and effect sizes at $N=1664$.

Power will be lower in the sample of smokers who do not meet all eligibility criteria for randomization to intensive treatment access (we estimate this to be roughly 416 participants, but may be as high as 800 participants), but this sample will be sufficiently large to generate

upper-bound estimates of effect sizes for intervention component, component-by-component interaction, and mediator and moderator effects.

July 2022 update to sample size based on recruitment challenges

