Initially, the sample size was N=1664 to provide adequate power to detect hypothesized effects (8% increments in treatment reach, or initiation of assisted quit attempts, and 8% increments in abstinence 2-years after enrollment). Given difficulties in recruitment using the current model, we recognize that this sample size is not feasible to achieve during the study period. As such, we have now revised our goals for this study and now propose a sample of 240-300 participants. This will ensure that at least 15 participants are in each cell of the experimental design, sufficient to yield stable estimates of effect sizes in this factorial design. Although this sample size will not provide adequate power to test hypothesized effects, it will be sufficient to generate effect size estimates and ranges, and to identify interventions and intervention combinations with promising effect sizes for future study.

H. Human Subjects Protections and Data Sharing

Describe any potential direct benefits to subjects. If there are no direct benefits, state this.

Every participant in the study will be given information about ways to access at least 1 evidence-based treatment to help them stop smoking and will be given access to that treatment at no direct personal cost (apart from possible telephone charges for telephone-delivered care such as cessation counseling and care management). Although smokers could access this care outside of the study, we know that only about 1-2% of smokers use a quit line and only about 5% use both medication and counseling. As such, the proposed study will offer all participants the benefit of information about treatment options and a low-barrier method of initiating treatment (i.e., by phone).

Describe the potential benefits of this research to society.

The proposed research also has the potential to benefit other smokers by identifying highly effective health system reach interventions that expand the reach of existing lower- and higher-intensity treatments and are feasible, cost-effective, and potentially sustainable in primary care settings. This work has the potential to accelerate the translation of clinical research on smoking interventions into healthcare practice and thereby reduce morbidity and mortality associated with smoking.

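### At N=240–300, 15 per cell is an average and not a floor, and the 16-term logistic model may have no finite fit and has no stated fallback; the ineligible sample is still sized at 416–800

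*Combined protocol and SAP*

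**What the plan says.** **Cell size and precision.** Power and Sample Size, July 2022 update: "This will ensure that at least 15 participants are in each cell of the experimental design, sufficient to yield stable estimates of effect sizes". It continues: "Although this sample size will not provide adequate power to test hypothesized effects, it will be sufficient to generate effect size estimates and ranges".

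**Model.** Analysis Plan, Aim 1: "all main and all 2-way, 3-way, and 4-way interactive effects will be tested as predictors in the logistic regression model". Aim 2, referring back to Aim 1: "effect coding will be used to ensure the independence of the main and interactive effects in this balanced design". Secondary Aim 1, on abstinence: "This analysis will estimate the main and interactive effects of the intervention components on end-of-study (2-year) 7-day point-prevalence abstinence rates". None of these says what is done if a cell has no events or only events.

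**Randomization.** Section D: "Randomization will be blocked by clinic, patient-identified gender, and eligibility for randomization to intensive treatment access", with no block size given. Section II has participants "recruited in 4-12 primary care clinics in 2 healthcare systems".

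**Planning values.** Power and Sample Size takes 8 percentage points as the increment of interest, with base rates of 5–65% for treatment use and 5–30% for abstinence.

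**Ineligible sample.** Power and Sample Size puts it at about 416, possibly 800, and calls it large enough for upper-bound estimates of component, interaction, mediator and moderator effects. Table 1 also has about 416. Section II says roughly 60, and Aim 2 says 30–60 with a maximum of 60. Section A keeps ceilings of 2600 overall and 1800 eligible, beside a target of 300.

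**The concern.** The update gives up adequate power for testing but claims that estimation is still sound, and it relies on that to pick components and combinations for further study. It offers no precision figure in support.

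The analysis model was written for 104 people per cell and was not revisited when cells shrank to 15–19. A saturated logistic model depends on the observed log-odds in every cell, so a single empty cell breaks it. If initiation is low, the primary Aim 1 fit as written may produce no usable coefficients, and a replacement model would then be chosen after seeing the data. The same applies to the abstinence model.

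**Working it through.** **1. The figure of 15.** 240/16 = 15.0, 300/16 = 18.75 and 1664/16 = 104. The plan's 15 is reproduced, as the mean at N=240. A minimum of 15 there requires exactly 15 in all 16 cells. Four to 12 clinics by two gender levels (assumed) give 8–24 strata, each of which can end in an incomplete block. Simulation used permuted blocks of 16 or 32; the block sizes, clinic sizes and gender split are assumptions.
- N=240: all cells reached 15 in 0 of 2,000 replicates in every setting.
- N=300: probability about 0.71–1.00 with blocks of 16, and as low as 0.15 with blocks of 32.
- Standard-error inflation from imbalance, √(N·Σ(1/n_cell)/256) − 1, was 0.2–2.3%.

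**2. The 16-term model.** Parameters: 1 + 4 + 6 + 4 + 1 = 16, for 16 cells. With effect coding each coefficient is (1/16)·Σ(±1)·log(p̂/(1−p̂)) over all 16 cells. One cell with p̂ = 0 or 1 therefore leaves no finite estimate for any term, main effects included. The probability of at least one such cell is

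P = 1 − Π[1 − (1−p)^n − p^n].

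Example: p = 0.20, n = 15. 0.8^15 = 0.0352, and 1 − (1 − 0.0352)^16 = 0.44.

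| Common rate | N=240 (15 per cell) | N=300 (12 cells of 19, 4 of 18) | N=1664 (104 per cell) |
|---|---|---|---|
| 5% | >0.99 | >0.99 | 0.07 |
| 10% | 0.98 | 0.91 | <0.001 |
| 15% | 0.77 | 0.54 | <0.001 |
| 20% | 0.44 | 0.22 | <0.001 |
| 30% | 0.07 | 0.02 | <0.001 |

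If all four components work, each adding 8 points (p = base + 0.08 × number of active components), N=240 gives:

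| Base rate | 5% | 10% | 20% | 30% | 40% | 60% | 65% |
|---|---|---|---|---|---|---|---|
| P | 0.74 | 0.40 | 0.07 | 0.01 | 0.01 | 0.53 | 0.87 |

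The rise at the top comes from cells in which everyone initiates: from a 65% base the fully active cell is at 97%.

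Aim 1 expects 25% missing follow-up. If missing counts as no treatment, true rates of 10, 20 and 30% become 7.5, 15 and 22.5%, and P at 15 per cell becomes 0.997, 0.77 and 0.30.

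Smaller models, simulated with no true effects: main effects plus 2-way terms had no finite fit in 0.55 (15 per cell) and 0.34 (19 per cell) of trials at 5%, and in 0.06 and 0.02 at 10%. Main effects alone failed in under 1% at 5% and never at 10%.

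**3. Precision.** Approximate 95% half-widths as risk differences, with balance, a common rate and complete data: 1.96√(4pq/N) for a main effect, 1.96√(16pq/N) for a 2-way difference in differences, and 1.96√(32pq/N) for cell versus cell.
- Narrowest (N=300, 5%): 4.9, 9.9 and 14.0 points.
- Widest (N=240, 50%): 12.7, 25.3 and 35.8 points.

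The cell-versus-cell formula is too narrow at 5%, where 0.95^15 = 0.46 of cells have no event. The Agresti–Caffo interval there averages about ±20 points at 15 per cell (against 15.6) and ±17 at 19 per cell. A fair cell-versus-cell range is ±17 to 36. Losing 25% of outcomes multiplies these widths by 1/√0.75 = 1.15.

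**4. Ineligible sample.** Eight cells: 30/8 = 3.75 and 60/8 = 7.5 per cell, against 416/8 = 52 and 800/8 = 100. At a 30% rate:

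| N | Main effect, 95% half-width | P(an all-or-none cell) |
|---|---|---|
| 30 | ±33 points | 0.93 |
| 60 | ±23 points | 0.44 |
| 416 | ±9 points | <0.001 |

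**The case against.** The update is candid that power is inadequate, and Table 1 calls the study a screening experiment that leads to an RCT. The stated target is 300, where a minimum of 15 is often met, and the imbalance is nearly harmless. The section on tailored outreach cites a 30% response to one registry campaign; at such a rate an empty cell is uncommon. The 416–800 figures are probably leftover text above a dated update, and they claim only upper-bound estimates.

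Most of this stands, and it limits the point. It does not remove it. The concession concerns testing, whereas the words at issue assert a guaranteed cell size and stable estimation. The 30% figure is one earlier result. The plan's own range starts at 5%, participants are not ready to quit within 30 days, and section H puts quit line use at 1–2% and combined medication and counseling at about 5%. The old ineligible-sample size still reads as current, and the update does not mention that sample.

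A reader might infer that Aim 1 will yield no estimates at all. The documents do not support that. The failure belongs to the logistic fit. Aim 1 also plans a difference in initiation rates, which is always finite, and a main-effects-only logistic model would rarely fail. Nor is failure of the 16-term fit a certainty for this trial, since the actual rate is unknown.

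**Conclusion.** The point holds in three parts of unequal weight.

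- **Wording.** *Ensure* is wrong at N=240 and not assured at 300, with little effect on precision. *Stable* is unsupported: half-widths of about 5–13 points (main effects), 10–25 (2-way) and 17–36 (cell versus cell) compare poorly with an 8-point effect of interest.
- **Model (the part that matters).** At common rates of 5–10% the 16-term fit very probably has no finite solution (0.91 or more at either N). At 20% the probability is 0.22–0.44. It is small for bases of about 20–40% when all four effects add up, and it rises again from high bases. It would therefore be wrong to infer that any rate above 30% is safe. The reduction in N created the exposure.
- **Ineligible sample.** The adequacy claim rests on about 7 to 27 times the people now planned (416/60 = 6.9; 800/30 = 26.7).

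The probabilities assume equal cells and either a common rate or additive 8-point effects. The cell-minimum results also depend on the assumed block sizes, clinic sizes and gender split. This should be corrected before the analysis; it does not invalidate the design.

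**What to change.** **July 2022 update.** Replace the guarantee with: an average of 15–19 per cell; individual cells may be smaller. Replace *stable* with approximate 95% half-widths as risk differences assuming complete data: main effect ±5 to 13 points, 2-way difference in differences ±10 to 25, cell versus cell ±17 to 36 (with a small-sample interval such as Agresti–Caffo at low rates). Note that 25% missing data would widen them.

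**Aims 1 and 2 and Secondary Aim 1.** Pre-specify what is done when any cell is all-or-none, for example Firth-penalised logistic regression with the same terms. In all cases report each component's marginal risk difference with its interval. Another named fallback would also do; what matters is that it is fixed in advance.

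**Power and Sample Size.** Delete the adequacy claim for the ineligible sample, or restate it as descriptive at N=30–60. Reconcile the sizes in Table 1, section A and the power section with section II and Aim 2.

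**Cost.** Wording and one fallback, with no added patients. The stated precision will look less favourable. Firth odds ratios shrink toward no effect at low rates: in simulation a true odds ratio of 2.84 (5% versus 13%) averaged 2.2–2.4, with no visible shrinkage at 20% versus 28%. The marginal risk difference was unbiased, with coverage of 0.95–0.97, which is why it should be reported alongside.
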